12.3.3.8. Mean Change from Baseline in EQ-5D assessment

The EQ-5D questionnaire is designed for self-completion by patients and will be administered at baseline, Week 9, Week 17, Week 28 and Week 52(or EOT). The EQ-5D-5L descriptive system, which will be applied in the study, comprises the following 5 dimensions: mobility, self-care, usual activities, pain/discomfort and anxiety/depression. Each dimension has 5 levels: no problems, slight problem, moderate problems, severe problems, and unable to/extreme problems. The questionnaire also includes a visual analogue scale, where the patient will be asked to rate current health status on a scale of 0-100, with 0 being the worst imaginable health state and 100 being the best imaginable health.

Descriptive statistics (frequency counts per answer) by treatment group will be presented for each of the EQ-5D dimension at each study visit.

The mean change from Baseline in EQ-5D-5L VAS score will be also summarized and analyzed. Baseline is defined as the last assessment before first intake of dose of study treatment. The analysis windows are defined in [Appendix 19.3.1](#).

A mixed model for repeated measures (MMRM) with treatment, visit, treatment*visit, and stratification factors as fixed effects, the baseline score value and baseline*visit interaction as covariate will be used to assess treatment difference. The analysis will include the patients with both a baseline and post-baseline value at the specific visit. The least-squares mean (LSM) and the corresponding 95% confidence intervals for the differences between roxadustat and the placebo group (roxadustat – placebo) will be presented along with the p-values for the treatment differences resulting from the model. An unstructured variance-covariance structure will be used for the within-patient variation. This variance-covariance matrix will be estimated across treatment groups. If the model fails to converge, then the covariance structure that converges and with the highest REML log likelihood will be used.

Missing value of this endpoint will be handled by the MMRM model, utilizing data from all visits and all patients.

Week 9 and week 52 are the analysis endpoint for 28-week and 52-week analysis, respectively. The p-value obtained will be reported.

This analysis will take into account the potential intercurrent events as follows:

1. Treatment discontinuation due to reasons other than AE/SAE: using Treatment-policy strategy: regardless of these intercurrent events occurred;
2. Treatment discontinuation due to AE/SAE: using Hypothetical strategy: A scenario is envisaged in which the patient suffers from the worst quality of life after discontinuation treatment due to AE/SAE. If

a patient discontinued treatment due to AE/SAE, all the missing EQ-5D-5L VAS scores afterward will be substituted with the worst possible scores before being used in descriptive summary and statistical models.

3. Death: using Treatment-policy strategy: regardless of these intercurrent events occurred. If a patient died, the EQ-5D-5L VAS scores up to death will be used for analysis.

Line plot of mean and mean change from baseline over time on EQ-5D assessment will be provided. A cumulative distribute plot will be presented to show the difference of patients achieving meaningful change in EQ-5D-5L VAS score between two treatment groups. A by-patient listing will also be provided.

The analysis will be conducted for FAS and PPS.

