12.3.2. Sequential Gatekeeping Procedure

Once the primary hypothesis has been rejected for the primary endpoint, the primary endpoint at week 52 and the secondary endpoints in the order specified in the Table 4 will be tested using a sequential gatekeeping procedure, in order to maintain the overall two-sided type I error of 0.05. If p-value from a test is < 0.05 , the claim of superiority will be considered successful, and the test will progress to the next comparison in sequence as follows.

Table 4: Sequential Gatekeeping Procedure

Test	Variable	Comparison
1	Proportion of patients who achieved TI ≥ 56 consecutive days (e.g., 8 weeks) since first dose in the first 28-weeks of treatment	Superiority of roxadustat versus placebo
2	Proportion of patients who achieved TI ≥ 56 consecutive days (e.g., 8 weeks) since first dose in the 52-weeks of treatment	Superiority of roxadustat versus placebo
3	Proportion of patients who achieved TI ≥ 56 consecutive days (e.g., 8 weeks) anytime during the study	Superiority of roxadustat versus placebo
4	Proportion of patients who achieved $\geq 50\%$ reduction in number of pRBC transfusions over 8 weeks compared to their Baseline for any 8-week period during the study	Superiority of roxadustat versus placebo
5	Cumulative number of patient-exposure-weeks (PEW) of TI over the first 28 weeks of the treatment period	Superiority of roxadustat versus placebo
6	Number of pRBC transfused change from baseline over the first 28 weeks of the treatment period	Superiority of roxadustat versus placebo
7	Proportion of patients who achieved TI for ≥ 20 consecutive weeks (140 consecutive Days)	Superiority of roxadustat versus placebo

8	Mean change from baseline in the PROMIS-SF v2.0 Physical Function 10b score at week 9	Superiority of roxadustat versus placebo
9	Mean change from baseline in the PROMIS-SF v1.0 Fatigue 13a score at week 9	Superiority of roxadustat versus placebo
10	Mean change from baseline in EQ-5D-5L VAS score at week 9	Superiority of roxadustat versus placebo

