12.3.3.6. Mean Change from Baseline in Physical Functioning Subscale of PROMIS

The PROMIS PF item measures self-reported, current capability to carry out activities that require physical actions, ranging from self-care (activities of daily living) to more complex activities that require a combination of skills, often within a social context. The questionnaire will be administered at the Week 1 Day 1, Week 9, Week 17, Week 28 and Week 52 (or EOT). The PF 10-item short form which contains 10 questions will be used in this study, and each item is scored on a 5-point rating scale, with higher scores indicating better functioning. To find the total raw score, sum the values of the response to each question, with the lowest possible raw score is 10; the highest possible raw score is 50.

PROMIS items are not scored as sums, but rather on a standardized T-score metric ([Appendix 19.5](#)) using IRT. The standardized norm-based T-scores will be used in the summary. The mean change from Baseline in the PROMIS-SF v2.0 Physical Function 10b score will be summarized and analyzed. A mixed model for repeated measures (MMRM) with treatment, visit, treatment*visit, and stratification factors as fixed effects, the baseline score value and baseline*visit interaction as covariate will be used to assess treatment difference. The LSM and the corresponding 95% confidence intervals for the differences between roxadustat and the placebo group (roxadustat – placebo) will be presented along with the p-values for the treatment differences resulting from the model. The LSM for the difference will be considered clinically meaningful if it exceeds the distribution-based minimal clinically important difference (MCID) and will be marked in the results, see [Section 19.8.1](#) for details of MCID. An unstructured variance-covariance structure will be used to model the within-patient errors. This variance-covariance matrix will be estimated across treatment groups. If the model fails to converge, then the covariance structure that converges and with the highest REML log likelihood will be used.

Missing values will be handled by the MMRM model, utilizing data from all visits and all patients.

A sensitivity analysis will be conducted using Analysis of Covariance (ANCOVA) model with Last Observation Carries Forward (LOCF) imputation, see [Section 19.8.3](#) for details.

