12.3.3.7. Mean Change from Baseline in Fatigue Subscale of PROMIS

Fatigue will be measured in the study using the 13-item fatigue scale of the FACIT Measurement System, each item is scored on a 5-point rating scale ranging from 1 to 5 depicting “not at all” to “very much”, with higher scores indicating better functioning. The questionnaire is designed for self-completion by patients and will be administered at baseline, Week 9, Week 17, Week 28 and Week 52(or EOT).

PROMIS items are not scored as sums, but rather on a standardized T-score metric ([Appendix 19.6](#)) using IRT. The standardized norm-based T-scores will be used in the summary. The mean change from Baseline in the PROMIS-SF v1.0 Fatigue 13a score over time will be summarized and analyzed using the FAS and PPS Population. The analysis window is defined in [Appendix 19.3.1](#).

A mixed model for repeated measures (MMRM) with treatment, visit, treatment*visit, and stratification factors as fixed effects, the baseline score value and baseline*visit interaction as covariate will be used to assess treatment difference. The LSM and the corresponding 95% confidence intervals for the differences between roxadustat and the placebo group (roxadustat – placebo) will be presented along with the p-values for the treatment differences resulting from the model. The LSM for the difference will be considered clinically meaningful if it exceeds the distribution-based minimal clinically important difference (MCID) and will be marked in the results, see [Section 19.8.1](#) for details of MCID. An unstructured variance-covariance structure will be used to model the within-patient errors. This variance-covariance matrix will be estimated across treatment groups. If the model fails to converge, then the covariance structure that converges and with the highest REML log likelihood will be used.

Missing value will be handled by the MMRM model, utilizing data from all visits and all patients.

A sensitivity analysis will be conducted using Analysis of Covariance (ANCOVA) model with Last Observation Carries Forward (LOCF) imputation, see [Section 19.8.2](#) for details.

Week 9 and week 52 are the analysis endpoint for 28-week and 52-week analysis respectively, the p-value obtained will be reported.

This analysis will take into account the potential intercurrent events as follows:

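### SAP 12.3.3.8 limits the EQ-5D VAS model to patients with a value at the specific visit; read literally, this conflicts with the section's own all-visits missing-data rule and should be deleted or reworded

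*SAP*

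**What the plan says.** SAP 12.3.3.8 analyses change from baseline in EQ-5D-5L VAS with an MMRM containing treatment, visit, treatment by visit, the stratification factors, baseline and baseline by visit. On covariance it states: "An unstructured variance-covariance structure will be used for the within-patient variation". Three further statements matter:

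- On who enters the model: "The analysis will include the patients with both a baseline and post-baseline value at the specific visit".
- On missing data: "Missing value of this endpoint will be handled by the MMRM model, utilizing data from all visits and all patients".
- On timing: "Week 9 and week 52 are the analysis endpoint for 28-week and 52-week analysis, respectively". A p-value is reported for each.

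The section also sets the intercurrent-event rules. Discontinuation for reasons other than AE/SAE follows treatment policy, with no substitution. For AE/SAE stoppers the rule is that if "a patient discontinued treatment due to AE/SAE, all the missing EQ-5D-5L VAS scores afterward will be substituted with the worst possible scores". For a patient who died, scores up to death are to be used.

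The PROMIS sections have the same model terms and unstructured covariance. SAP 12.3.3.6 says "Missing values will be handled by the MMRM model, utilizing data from all visits and all patients", and 12.3.3.7 says "Missing value will be handled by the MMRM model, utilizing data from all visits and all patients". Neither restricts patients to those with a value at a given visit.

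In SAP Table 4 (12.3.2), Test 10, the last of ten, is "Mean change from baseline in EQ-5D-5L VAS score at week 9". EQ-5D at Week 52 is not in that table, although SAP 12.1 counts 52-week results among those used to judge efficacy.

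**The concern.** The purpose of an MMRM here is that a patient without a score at the tested visit still contributes through the visits that were observed. The inclusion sentence, taken at its word, excludes that patient, and a later paragraph of the same section puts the patient back. Two programmers could build two patient sets and obtain two p-values, including for a gatekept test.

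The effect would also depend on why a patient stopped. An AE/SAE stopper keeps a value through worst-score substitution and stays in. A patient who stopped for another reason, or died, with no Week 52 value leaves the Week 52 analysis altogether. This sits badly with the treatment-policy strategy and with the instruction to use scores up to death.

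EQ-5D also has less behind it than PROMIS. The LOCF sensitivity analysis in SAP 19.8.2 covers only Physical Function and Fatigue. Beyond the AE/SAE substitution, the MMRM is the only missing-data method stated for EQ-5D.

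**Working it through.** The plan gives no EQ-5D figure to reproduce: no SD, effect, power or missing rate. The check is therefore one of logic, followed by an illustration on stated assumptions.

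**1. Who can lack a value at the tested visit.** Windows are from SAP Table 7.7.

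- Week 9: scheduled day 7 × (9 − 1) + 1 = 57. The window runs from Day 1 post-dose to before Day 57 + 28 = 85, that is, through Day 84.
- Week 52: scheduled day 7 × 52 + 1 = 365. The window opens on Day 365 − 84 = 281.
- Protocol Appendix B collects HRQoL after an early stop at EOT and at Post-EOT Week 4, with no entry in the 8-weekly column. SAP 19.3.1 keeps follow-up assessments outside the windows.

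A non-AE discontinuer whose EOT falls before Day 281 therefore has no Week 52 value. The supplied protocol is Amendment 02 and the SAP is based on Amendment 03, so this schedule may have changed.

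**2. What the restriction does to the model.** Suppose every included patient has the target-visit value. The likelihood factors into the target visit given covariates, times the other visits given the target visit and covariates. With unstructured covariance and covariates crossed with visit, the second factor carries no information on the target-visit contrast. The estimate is then ANCOVA on patients with a value at that visit. The SAP does not cross the stratification factors with visit, so with those terms the equality is near rather than exact.

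**3. Illustration.** From the documents: 140 patients enrolled (SAP 17) at 3:2, giving 140 × 3/5 = 84 and 140 × 2/5 = 56. Assumed: VAS SD 18, true effect 5 at every visit, correlation 0.6 for Week 9 and 0.5, 0.6 or 0.7 for Week 52, no stratification factors and no worst-score substitution. There were 400 trials per scenario, fitted by maximum likelihood. The simulation error of each mean is about 0.13 to 0.17.

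Week 9, missing at random at that visit only:

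| Missing | Patients of 140 | All-visit MMRM (SE) | Restricted MMRM (SE) | SE ratio |
|---|---|---|---|---|
| 5% | 7 | 5.01 (2.55) | 4.98 (2.56) | 1.004 |
| 10% | 14 | 5.10 (2.61) | 5.12 (2.65) | 1.015 |
| 20% | 28 | 4.80 (2.65) | 4.79 (2.73) | 1.030 |

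Week 52, with dropout after each visit following a logistic model in the last score (slope 1 per SD). Intercepts were −2.6 for roxadustat and −1.8 for placebo in the first case, and −2.0 for both arms in the second:

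| Dropout rule | Missing, roxadustat vs placebo | Correlation | All-visit | Restricted | Difference |
|---|---|---|---|---|---|
| Differs by arm | 21% vs 43% | 0.5 | 5.01 | 3.97 | 1.04 |
| Differs by arm | 21% vs 42% | 0.6 | 4.92 | 4.00 | 0.92 |
| Differs by arm | 20% vs 42% | 0.7 | 4.94 | 3.95 | 0.99 |
| Same in both arms | 32% vs 38% | 0.5 | 5.24 | 4.96 | 0.28 |
| Same in both arms | 32% vs 38% | 0.6 | 4.94 | 4.62 | 0.32 |
| Same in both arms | 31% vs 37% | 0.7 | 4.92 | 4.61 | 0.31 |

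In the last three rows the rates differ only because the treatment effect raises scores. With no true effect and the same rule in both arms, the arms are exchangeable and the restricted contrast is unbiased by symmetry. In every scenario the restricted MMRM matched ANCOVA on patients observed at the visit to two decimals, as step 2 predicts.

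**The case against.** The strongest reply is that the sentence can be read at the level of records: a change score enters at a visit only if there is a baseline and a value at that visit. That is ordinary MMRM and agrees with the missing-data sentence, the visit interactions and the unstructured covariance. This stands as a possible reading, so the consequences are conditional and it cannot be said that the two sentences are irreconcilable. But the sentence speaks of patients rather than records, adds nothing on the milder reading, and is absent from PROMIS. It still needs rewording.

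A reader might infer more than the documents support:

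- *That Week 52 becomes a complete-case analysis.* AE/SAE stoppers remain through substitution; those lost are other discontinuers and deaths without a value.
- *That the restricted analysis needs data missing completely at random.* It does not. Missingness that depends only on arm, baseline or strata does no harm to an adjusted comparison. The harm comes from dependence on earlier post-baseline scores.
- *That the restriction favours roxadustat.* In the assumed scenarios the shift is against it, so the chance of a false superiority claim would not rise.
- *That a confirmatory claim is in serious doubt.* Week 52 EQ-5D is outside Table 4, and no test follows Test 10. Missing Week 9 means having no VAS score from first dose through Day 84, which may be rare.

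It is also fair that every size rests on outside assumptions.

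**Conclusion.** The point holds in conditional form. SAP 12.3.3.8 contains an inclusion sentence that, read literally, conflicts with its missing-data sentence and departs from the PROMIS sections without a stated reason. If it governs, the MMRM loses its handling of missing scores at the tested visit, for those patients whose scores are not substituted.

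At Week 52 the reported, non-gatekept comparison could be biased if non-AE dropout or death differs by arm and depends on earlier scores. Under the assumptions above, the shift is about 1 point of a true 5 with roughly 21% versus 43% missing. It is 0.5 points or less with 32% versus 38%, and none under identical dropout with no true effect. The actual size cannot be derived from the documents, and the illustration omits the worst-score substitution.

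At Week 9 the consequence for Test 10 is a loss of precision of about 3% in SE or less, with no added bias when the score is missing at random, plus uncertainty about which patients are analysed. The stakes are modest, but the patient set for a gatekept test should not be open to interpretation.

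**What to change.** Delete the restricting sentence in SAP 12.3.3.8. Alternatively, replace it with: *the model includes all patients in the analysis set with a baseline and at least one post-baseline EQ-5D-5L VAS score, using all visits.* The at-least-one criterion is a clarification consistent with the all-visits, all-patients sentence; the PROMIS sections do not themselves state it. If the record-level meaning was intended, the replacement wording says so clearly.

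The cost is one sentence in the SAP before database lock. No new data are needed, and neither the model nor the testing sequence changes.

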12.3.4. Analysis of Exploratory Efficacy Endpoints

P values generated from treatment comparison for exploratory endpoints are exploratory, no multiplicity adjustment will be needed. Nominal p-values are used primarily as measures of strength of association rather than formal criteria to claim statistical significance. The nominal p-values will also be explained in table footnotes. All analysis will be performed using the FAS.

12.3.4.1. Time to transfusion independence (TI)

Time to transfusion independence (in weeks) is measured from the day of first study drug to the first day of TI response anytime during the study or a censor date. [Section 12.3.3.1](#) for the detail of definition of TI response anytime during the study. If a patient has more than one at least 56-day period with transfusion free, that is, more than one TI response period, only the first will be used for analysis.

- for those who have a TI response period, time to transfusion independence will be calculated as duration = first day of TI response - day of first study drug +1 where the first day of TI response is defined as the first day of at least 56-day transfusion-free period
- for those who do not have a TI response period, time to transfusion independence will be calculated as duration = date of the end of study or treatment discontinuation due to AE/SAE or death, whichever comes earlier - day of first study drug + 1.

Median time to transfusion independence will be estimated using Kaplan-Meier (K-M) method and its associated 2-sided 95% CIs for each treatment group will be calculated using the method of Brookmeyer and Crowley. The estimated survival probability and its associated 2-sided 95% CIs for each treatment group up to 52 weeks by every 4-weeks will be estimated by Kaplan-Meier product limit method. Kaplan-Meier curves will also be presented by treatment group.

Sample SAS codes are presented as below:

```
PROC LIFETEST DATA= PLOTS=SURVIVAL;
```

```
    TIME value*censor (1);
```

```
STRATA treatment;
```

```
SURVIVAL OUT=xx;
```

```
RUN;
```

Treatment comparison will be performed using the stratified log-rank test stratified by randomization factors.

Sample SAS codes are presented as below:

```
PROC LIFETEST DATA=;  
    TIME value*censor (1);  
    STRATA <stratum_var>/GROUP=treatment;
```

```
RUN;
```

Time to transfusion independence will be compared between treatment groups using the Cox regression model, controlling for baseline hemoglobin and the stratification factors. Two-sided 95% CI of the hazard ratio will be presented for the treatment difference.

Sample SAS codes are presented as below:

```
PROC PHREG DATA=;  
    MODEL value*censor (1)= treatment base_hb <stratum_var>;
```

```
RUN;
```

Model checking: The proportional hazards assumption will be checked graphically using a log-cumulative hazard plot against log-survival time. This plot will give approximately parallel lines if the proportional hazards assumption between treatment arms subgroups holds. If the proportional hazard assumption is violated, then stratified Cox Model (with stratification-factors in STRATA statement) will be used instead.

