12.3.3. Analysis of Secondary Efficacy Endpoints

All secondary endpoints measured for treatment periods will be analyzed both for the first 28 weeks of treatment and for 52-week study treatment period. Others will be analyzed for the time during the study. The secondary efficacy endpoints will be analyzed based on the FAS population unless it is specified otherwise. Analyses using the PPS will be used as sensitivity analyses.

12.3.3.1. Proportion of Patients who achieved TI ≥ 56 consecutive days anytime during the study

The proportion of patients who achieved TI for ≥ 56 consecutive days will be summarized using the FAS and PPS and will be compared between the two treatment groups. TI is defined as the absence of any intravenous RBC transfusion (packed cell or whole blood) during any consecutive 56 days anytime during the study. TI will be estimated in the duration beginning with the first dose date (Day 1) and ending with the end of study or treatment discontinuation due to AE/SAE or death, whichever comes earlier. RBC transfusions after end of treatment will be recorded on CRF until the last visit at week 52 from first dose and will be used to define TI.

The p-value obtained will be reported for the test of the null hypothesis that there is no difference between the two treatment groups.

Similar methods will be used as for the primary endpoint.

This analysis will take into account the potential intercurrent events as follows:

1. Treatment discontinuation due to any reasons: using Treatment-policy strategy: regardless of these intercurrent events occurred; the TI will be estimated using RBC transfusion records in the whole study duration.
2. Death: using Treatment-policy strategy: regardless of these intercurrent events occurred; Patients who died prior to week 8 will be classified as non-responders. TI will be estimated using RBC transfusion records for the study duration up to death.

12.3.3.2. Proportion of Patients Who Achieved $\geq 50\%$ Reduction in Number of pRBC Transfusions over 8 Weeks Compared to Their Baseline for Any 8 Week Period during the Study (Factor of Erythroid Response)

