12.3.4.2. Time to 50% reduction in pRBC transfusion

Time to 50% reduction in pRBC transfusion (in weeks) is measured from the day of first study drug to the first day of response of 50% reduction of pRBC transfusion or a censor date. See [Section 12.3.3.1](#) for the detail of definition of the response.

- for those who have a response, time to 50% reduction in pRBC transfusion will be calculated as duration = first day of response - day of first study drug + 1
- for those who do not have a response, time to 50% reduction in pRBC transfusion will be calculated as duration = date of the end of study or treatment discontinuation due to AE/SAE or death, whichever comes earlier - day of first study drug + 1.

Median time to 50% reduction in pRBC transfusion will be estimated using Kaplan-Meier (K-M) method and its associated 2-sided 95% CIs for each treatment group will be calculated using the method of Brookmeyer and Crowley. The estimated survival probability and its associated 2-sided 95% CIs for each treatment group up to 52 weeks by every 4-weeks will be estimated by Kaplan-Meier product limit method. Kaplan-Meier curves will also be presented by treatment group.

Sample SAS codes are presented as below:

```
PROC LIFETEST DATA= PLOTS=SURVIVAL;  
    TIME value*censor (1);
```

```
STRATA treatment;
```

```
SURVIVAL OUT=xx;
```

```
RUN;
```

Treatment comparison will be performed using the stratified log-rank test stratified by randomization factors.

Sample SAS codes are presented as below:

```
PROC LIFETEST DATA=;  
    TIME value*censor (1);  
    STRATA <stratum_var>/GROUP=treatment;
```

```
RUN;
```

Time to 50% reduction in pRBC transfusion will be compared between treatment groups using the Cox regression model, controlling for baseline hemoglobin and the stratification factors. Two-sided 95% CI of the hazard ratio will be presented for the treatment difference. Sample SAS codes are presented as below:

```
PROC PHREG DATA=;  
    MODEL value*censor (1)= treatment base_hb <stratum_var>;
```

```
RUN;
```

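### Time to TI and time to 50% transfusion reduction censor deaths under Kaplan-Meier, so one minus the curve overstates the share of patients who respond

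*SAP*

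**What the plan says.** **Event.** SAP 12.3.4.1 measures time from first dose to the "first day of TI response anytime during the study or a censor date". The event is dated back to the start of the qualifying period, "where the first day of TI response is defined as the first day of at least 56-day transfusion-free period".

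**Patients without a response.** In both 12.3.4.1 and 12.3.4.2 their time is "date of the end of study or treatment discontinuation due to AE/SAE or death, whichever comes earlier - day of first study drug" plus one day. The sample code carries a single censoring flag. Neither section names a competing event or a cumulative-incidence method.

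**Outputs.** Section 12.3.4.1 states: "Median time to transfusion independence will be estimated using Kaplan-Meier (K-M) method". It then asks for "The estimated survival probability and its associated 2-sided 95% CIs for each treatment group up to 52 weeks by every 4-weeks", with curves. Section 12.3.4.2 repeats the scheme: "Median time to 50% reduction in pRBC transfusion will be estimated using Kaplan-Meier (K-M) method". For the comparison, "Treatment comparison will be performed using the stratified log-rank test stratified by randomization factors", followed by a Cox model.

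**The response definition being borrowed.** Section 12.3.4.1 points to 12.3.3.1, which says two things. Its definition paragraph ends the TI window at AE/SAE discontinuation, death or end of study. Its intercurrent-event list, like Table 1 in 4.2.2, applies treatment policy to discontinuation for any reason and uses records from the whole study. It also says "RBC transfusions after end of treatment will be recorded on CRF until the last visit at week 52 from first dose" and that these count towards TI. Patients who die before Week 8 are non-responders. Section 12.3.3.2 contains the same pair of statements for the 50% reduction.

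**Status.** The opening of 12.3.4 makes these endpoints exploratory with nominal p-values. They are not in Table 4, and section 17 says they were added out of clinical interest.

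**The concern.** Kaplan-Meier lets a censored patient stand for someone who will respond later at the rate seen in those still followed. That is reasonable for a patient whose follow-up simply ends. It is not possible after death. The weight of each dead non-responder is passed to patients still at risk, so one minus the curve estimates response in a population where nobody dies.

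Discontinuation for an AE is less clear, because the SAP gives two answers. If the window closes at the AE stop, that patient has finished without a response, and censoring has the same effect as for death. If treatment policy applies, the patient is still observed and can still respond, and censoring discards data that the plan collects.

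At stake is the reading of two displays. The binary table in 12.3.3.1 keeps these patients in the denominator and the curve does not, so the two would give different response probabilities for the same patients. A reported median could also come out too early, or appear where fewer than half respond.

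**Working it through.** **1. Inputs.** The plan states no figure for these outputs, so there is none to reproduce. The nearest is the SAP 3.2 power statement (120 patients, 3:2, 56% versus 13%, at least 90%). Exact two-sided Fisher power for 72:48 is 99.9%, which is consistent. Its rates, which belong to the primary endpoint, are borrowed below as an assumption. The documents give no rates of death or AE discontinuation, so these are varied over a range.

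**2. Direction.** With nobody removed before the last response, one minus Kaplan-Meier (1-KM) equals the observed share. Every removal that precedes a later response raises it. So 1-KM is never below the observed share, and equals it only if removals come after the last response.

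**3. Effect on whether a median is reported.** SAP 17 gives 140 patients, so 140 × 3/5 = 84 on roxadustat. Suppose 32 respond before Week 10, 13 are then removed without response, and 8 respond later.
- Observed share: 40/84 = 47.6%, so there is no median.
- 1-KM = 1 − (52/84) × (31/39) = 50.8%, so a median is reported.

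**4. Constant hazards over 52 weeks.** Let r be the share responding and q the share removed first. The total hazard is H = −ln(1 − r − q)/52 and the response hazard is h = H × r/(r + q). Hence 1-KM = 1 − (1 − r − q)^(r/(r + q)). A competing-risks estimate gives r.

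| q | 1-KM, r = 56% | excess (points) | 1-KM, r = 13% | excess (points) |
|---|---|---|---|---|
| 5% | 57.9% | 1.9 | 13.4% | 0.4 |
| 10% | 60.0% | 4.0 | 13.7% | 0.7 |
| 20% | 65.1% | 9.1 | 14.6% | 1.6 |
| 30% | 72.2% | 16.2 | 15.6% | 2.6 |

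Effect on the median at r = 56%, q = 10%: H = 1.0788/52 = 0.02075 and h = 0.01760 per week. The Kaplan-Meier median is ln 2/h = 39.4 weeks. Cumulative incidence reaches 50% when 1 − exp(−Ht) = 0.5 × 0.66/0.56 = 0.589, that is t = 0.890/0.02075 = 42.9 weeks.

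**5. Patient-level simulation of the TI rule.** Constant hazards do not reflect the back-dated 56-day event, so the rule was simulated with 20,000 patients per scenario. TI needed at least 56 transfusion-free days before removal or day 364. The event was dated to the first of those days, and all others were censored at removal or day 364. Assumptions: latent response 60% (active-like) or 15% (placebo-like); median onset 14, 56 or 120 days; before onset, fairly regular transfusions at about 2.5 per 8 weeks; 10% to 30% removed by death or AE stop by Week 52; removal ends the chance of response. Excess of 1-KM over the observed share, in points:

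| Arm, median onset | 10% | 20% | 30% |
|---|---|---|---|
| Active-like, 14 d | 0.4 | 0.7 | 1.2 |
| Active-like, 56 d | 1.2 | 2.7 | 4.0 |
| Active-like, 120 d | 1.6 | 3.2 | 5.0 |
| Placebo-like, 14 d | 0.1 | 0.2 | 0.3 |
| Placebo-like, 56 d | 0.3 | 0.6 | 0.9 |
| Placebo-like, 120 d | 0.4 | 0.8 | 1.3 |

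In the active-like arm with 120-day onset and 10% removed, the observed share is 48.7% and 1-KM is 50.3%, so the median problem of step 3 appears here too. The 50% reduction endpoint was not simulated. The direction argument in step 2 applies to it unchanged.

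**6. Which arm.** From step 4, 56% response with 10% removed is overstated by 4.0 points, and 13% response with 20% removed by 1.6. The arm with fewer removals has the larger absolute gap. In relative terms the order reverses: 4.0/56 = 7% against 1.6/13 = 12%.

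**The case against.** The share who respond is already reported properly elsewhere. Fixed-denominator proportions with exact intervals and CMH tests are planned, and no claim rests on the time-to-event displays. The gap is also small beside sampling error: the 95% half-width for 50% of 84 is 1.96 × √(0.25/84) = 10.7 points. Both statements stand, and they set the severity. They do not remove the bias, which is systematic and avoidable.

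The size depends on timing. With 84 patients, 32 early and 10 late responders and 10% (8.4) removed in between, 1-KM is 1 − (52/84)(33.6/43.6) = 52.3% against 50.0% observed. If 5 of the 10 respond before the removals, it is 1 − (47/84)(33.6/38.6) = 51.3%. If all 10 do, the excess is zero. This stands, and is why a range is given.

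Closing the window at an AE stop can be defended as a choice of estimand. Protocol 3.4.5 prohibits agents such as those intended to treat MDS only through the End of Treatment visit, so later transfusion independence may reflect other therapy. That also stands. But the SAP has not made the choice consistently, and even with a closed window, censoring followed by Kaplan-Meier is the wrong estimator of the share who respond.

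Three stronger readings are tempting and not supported:
- That the method always favours the arm with more deaths and AE stops. This needs equal response rates and timing; step 6 gives a counterexample in absolute points.
- That AE discontinuers are known non-responders. Under the treatment-policy wording they remain observed and may respond.
- That the treatment comparison is invalid. The log-rank test and the Cox hazard ratio remain interpretable as cause-specific comparisons.

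**Conclusion.** The point holds for the Kaplan-Meier outputs of both endpoints. Censoring at death makes one minus the curve overstate the cumulative share who respond, and can make the median too early or produce one where fewer than half respond. The SAP plots survival probability, so the overstated quantity is its complement.

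Under the TI rule, with 10% to 30% death or AE stops, the excess is about 0.4 to 5.0 points in an active-like arm and 0.1 to 1.3 in a placebo-like arm. Constant hazards give more, but ignore the back-dated event. These sizes rest on assumed removal rates, onset times and transfusion pattern, and on AE stops ending the chance of response. For deaths alone the direction is certain. For AE stops it is certain only if the window closes at the stop.

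Severity is low: both endpoints are exploratory with nominal p-values.

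**What to change.** 1. In 12.3.3.1 and 12.3.3.2, reconcile the window that ends at AE/SAE discontinuation with the treatment-policy wording there and in Table 1, and carry the answer into 12.3.4.1 and 12.3.4.2. If treatment policy is kept, follow AE discontinuers to end of study using their recorded transfusions. If the window closes at the AE stop, code that stop as a competing event.
2. In 12.3.4.1 and 12.3.4.2, code death without response as a competing event. Report Aalen-Johansen cumulative incidence curves, four-weekly probabilities and medians by arm in place of Kaplan-Meier. A median is then given only if cumulative incidence reaches 50%.
3. Keep the stratified log-rank test and the Cox model, labelled cause-specific. Gray's test is optional.
4. While editing, correct the cross-reference in 12.3.4.2: it cites 12.3.3.1, but the 50% reduction response is defined in 12.3.3.2.

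The cost is SAP wording and minor programming, with no new data. Displayed response probabilities may be slightly lower. If AE discontinuers are followed to end of study, some may add responses, so the net change for them cannot be told in advance.
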